3.3 Breaking the blind

In the event of any serious adverse effects that are deemed to be a direct result of the treatment, the examining neurologist or DSMB may request for the patient to be un-blinded.

4. Subject Selection:

Fifty subjects for this study will be selected based upon their clinical disease status. Only patients with primary progressive or secondary progressive MS who have significant disability (EDSS between 3.0 and 6.5) that was not acquired within the last 12 months will be eligible. Patients should have a relatively stable disease state (duration of MS \leq 20 years at time of screening), which will allow better discernment between natural disease progression and treatment-related events. Disease stability will be determined by less than a 1.0-point change in EDSS in the last 12 months, and lack of gadolinium-enhancing lesions on an MRI and by a stable MRI disease burden (number and size of T2 lesions) in the last six months.

Enrollment criteria will also include specific clinical phenotypes which showed preliminary evidence of improvement during Phase I testing. Patients with symptomatic evidence of bladder dysfunction will be enrolled, and urodynamics testing will be conducted before and after treatment.

Exclusion criteria includes patients who have taken systemic chemotherapeutic or anti-mitotic agents within three months of the study start date due to possibility of interference with the bone marrow procedure and the potential negative impact on MSC-NP viability. Because of the experimental nature of this treatment, we are excluding patients who may be at greater risk for complications. Patients with central nervous system infections and blood diseases are at particular risk due to the route of administration of cells and the invasive nature of bone marrow aspiration. Patients who are anticipated to have difficulty accessing the intrathecal space related to scoliosis, obesity, or any other relevant factors determined by the PI. Participation in the trial will be terminated if a subject meets any of the exclusion criteria during the

course of the study. Detailed description of inclusion/exclusion criteria for this study will be provided in the clinical protocol.

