5.7 MRI Protocol

Brain, cervical and thoracic spine MRI scans will be scheduled at baseline, and at months 13, 27, and 36 using 3Tesla Siemens MAGNETOM VERIO scanners. Assessments will include the following:

- Proton density and T2-weighted two-dimensional (2D) multislice turbo/fast spin-echo
- T1-weighted three-dimensional (3D) spoiled gradient recalled echo both pre-contrast and after a 10 minute delay following injection of gadolinium post-contrast sequencing
- 2D T2 weighted Fluid -Attenuated Inversion Recovery (FLAIR)
- MTR MR tractography dependent on the number of tracts followed
- DTI – A T2 SPC 3D Flair sagittal sequence, EP diffusion, and a gradient filed mapping

Using the CorTechs NeuroQuant software package a multi-structure atrophy report will be generated for all brain MRI scans as well as a Lesion Quant Flair assessment of total number and volume of lesions; the total number and volume of enlarging lesions and the total number and volume of new lesions.

All lesions to be counted would have to be at least 3 voxels in size. For lesions to be considered enhancing an increase in intensity by at least 20% on the post-contrast images compared to the baseline T1 sequence lesions.

The total number of new or enlarging T2 hyperintense lesions as detected by MRI will be assessed by a negative binomial model. Percentage change in total brain volume from baseline will be assessed using an MMRM analysis.

6. Research Study Procedures:

Please see Schedule of activities (Study Table) Section 6.4 for the schedule of assessments performed during the study.

6.1 Screening procedures (Month 4; within 4 months prior to first treatment):

- Candidates believed to meet the inclusion/exclusion criteria will first attend a pre-enrollment visit where the details of the informed consent form (ICF) will be explained in depth.

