- Subjects will be told that their participation is voluntary and that their regular MS treatment will continue whether or not they enter the study. Consent for participation in the study will be obtained by any of the examining neurologists, the clinical trials manager, or by one of the study nurses, and documented in the subject's study file during the initial screening visit. An explanation and justification for the study will be given to the participant at this time. Consenting will occur after having had ample time to read the ICF, speak to family and friends, and review the consent with and ask questions of the consenting neurologist or study nurse. Patients will be given a copy for their records.
- Subjects will then undergo the following examinations to confirm eligibility for study participation
 - Complete physical examination with vital signs
 - Complete neurological examination
 - EDSS
 - Infectious Disease Questionnaire
 - Pregnancy test (for female patients of child-bearing age)
 - Infectious disease testing including HIV Test
 - Urine tests for drug/nicotine abuse (In addition to the screening period, a drug/nicotine urine test could be done at any time during the study for random testing)
- The EDSS evaluations will be done by the examining neurologists at Tisch MSRCNY. Every attempt will be made to have the same examining neurologist for each patient for the study duration. Examining neurologists will perform objective physical and neurological examinations during the study to evaluate efficacy, and will be blinded to the treatment
- All patients will be required to go to a clinical laboratory facility to undergo a panel of infectious disease screening. The results will be sent to the screening neurologist, and any patient positive for any infectious diseases will be excluded from the study.
- Screening Blood Draw
- The initial screening will last 1 hour.

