6.2 Study drug procedures

Bone Marrow Visit (Month -3):

- This visit will occur approximately one month after enrollment and approximately 3 months prior to the first treatment.
- Vital signs will be documented
- A bone marrow aspiration will be performed by [name], an experienced, board certified hematologist affiliated with the Tisch MSRCNY. [name] will obtain a bone marrow aspirate from the sternum or the iliac crest under sterile conditions following standard procedure. An adult bone marrow kit with a heparinized syringe will be used.

- Bone marrow aspirate will be obtained from the manubrium of the sternum, at the level of the second intercostal space. Alternatively, aspirate may be obtained from the iliac crest. Bone marrow will be aspirated using an adult bone marrow kit with a heparinized syringe.
- Each research subject's sterile bone marrow sample will be placed in a pre-labeled bag and immediately transferred from the clinic to the stem cell culture laboratory. Patients will be told not to shower or get their bandage wet for 24 hours following the procedure. In order for patients to move to the next phase of the study, their cells must be viable and pass bone marrow release testing. If for some reason cells do not thrive, the patient's involvement in the study will be reevaluated.
- Total duration of the Bone Marrow Visit is approximately 2 hours and will be conducted at the Tisch MSRCNY due to necessary proximity to the cell manufacturing laboratory.
- Cells from subjects who have had bone marrow harvested under the long-term ongoing research protocol, "Harvesting Bone Marrow for Neural Stem Cells" (Former St. Luke's-Roosevelt IRB# 08-049) (Current WIRB# 20162012), can be used for implantation as long they are deemed acceptable for use (and eliminate any risk from an unnecessary marrow harvesting procedure). This includes bone marrow harvested under this long-term ongoing research protocol harvested prior to enrollment in this study.

Baseline Visit (Month-1; within one month prior to first treatment):

- The purpose of the baseline visit is to establish baseline values of outcome assessments prior to treatment.
- The following baseline visit exams will be conducted by study subject's examining neurologist and study coordinator (duration approximate 1 hour)
 - Vital signs-Only if not performed at screening
 - Physical exam-Only if not performed at screening
 - Neurological exam-Only if not performed at screening
 - Headache pain scale

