 - EDSS-Only if not performed at screening
 - MSFC
 - 6 Minute Walk Test
 - 12 Item MS Walking Scale
 - Bladder Survey
 - Urinalysis and Culture to screen for UTI
- The following exams will be scheduled to occur within one month prior to the first treatment
 - MRI (brain, C and T spine) ± Gadolinium enhancement
 - Urodynamic testing of bladder compliance (ability of bladder to fill without accompanying rise in bladder pressure)

Treatment Phase visits, year 1 (Month 0, 2, 4, 6, 8, and 10):

- Treatment/placebo visits will be conducted at the Tisch MSRCNY every 2 months (\pm 1 week)
- Details regarding treatment/placebo procedures detailed in section 5.2.2 above
- Treatment visits will be conducted by the treating neurologist, [name]
- Duration of treatment visits will last approximately 5 hours
- Study subjects will be instructed to stay in bed and limit any physical activity for the 24 hours following each procedure.
- CSF for biomarker analysis discussed in 5.2.2
- Blood draw for serum and plasma biomarker analysis
- Vital Signs
- EDSS and MSFC (Month 6 Only) Follow-up by phone will occur 48 hours, 1 week and 1 month after each treatment visit. The purpose of the follow-up phone call is safety assessment and to document any adverse events. Calls will be made either by the clinical trial manager, the clinical research assistants, or the adverse event physician. Assessment will include the following:
- Headache pain scale

Outcome assessments I (Month 13)

- The purpose of outcome assessment I visit is to evaluate effects of the treatment compared to the baseline visit, as well as to serve as a baseline visit for the crossover treatment phase.
- The following exams will be conducted 3 months following the 6th treatment phase visit (\pm 1 week)
 - Vital signs
 - Physical exam
 - Neurological exam
 - Headache pain scale
 - EDSS
 - MSFC
 - 6 Minute Walk Test
 - 12 Item MS Walking Scale
 - Bladder Survey
 - Urinalysis and Culture to screen for UTI
- The following exams will be scheduled to occur 3 months following the 6th treatment visit (\pm 1 week)
 - MRI (brain, C and T spine) \pm Gadolinium enhancement
 - Urodynamic testing of bladder compliance (ability of bladder to fill without accompanying rise in bladder pressure)

Treatment Phase visits, year 2 (Month 14, 16, 18, 20, 22, and 24):

- Crossover treatment/placebo visits will be conducted at the Tisch MSRCNY every 2 months (\pm 1 week)

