6.4 Schedule of activities (Study Table)

| Tests and Assessments | Pre-treatment Phase | | | Treatment Phase, year 1 ² | | Safety FU | Outcome assessments I ³ | Treatment Phase, year 2 ² | | Safety FU | Outcome assessments II ² | Final FU ³ |
|--|--|-------------------------------|----------------------------|---|---|---|------------------------------------|---|---|--|-------------------------------------|------------------------------------|
| | Screening Visit Month -4 (Within 4 months prior to treatment phase) | Bone marrow visit Month -3 | Baseline visit Month -1 | Treatment group Months 0, 2, 4, 6, 8, 10 | Placebo group Months 0, 2, 4, 6, 8, 10 | FU by phone 48 hrs and 1 week after each treatment or placebo | All groups Month 13 | Treatment group (crossover from placebo) Months 14, 16, 18, 20, 22, 24 | Placebo group (crossover from treatment) Months 14, 16, 18, 20, 22, 24 | Follow-up by phone 48 hrs and 1 week after each treatment or placebo | All groups Month 27 | End of study follow-up Month 36 |
| ICF | X | | | | | | | | | | | |
| Serum and Plasma Biomarker Analysis Blood draw | | | | X | X | | | X | X | | | X |
| Screening Blood Draw ⁴ | X | | | | | | | | | | | |
| Bone marrow aspiration | | X | | | | | | | | | | |
| LP Procedure | | | | X | X | | | X | X | | | X |
| CSF aspiration for biomarker analysis | | | | X | X | | | X | X | | | X |
| Vital signs | X | X | X ⁵ | X | X | | X | X | X | | X | X |
| Physical exam | X | | X ⁵ | | | | X | | | | X | X |
| Neurol. exam | X | | X ⁵ | | | | X | | | | X | X |
| Headache pain scale | | X | | | X (12 total) | X | | | X (12 total) | X | X | |
| EDSS | X | | X ⁵ | X ⁶ | X ⁶ | | X | X' | X' | | X | X |
| MSFC (T25FW, 9HPT, PASAT) | | | X | X ⁶ | X ⁶ | | X | X ⁷ | X ⁷ | | X | X |
| 6 Minute Walk Test (6MW) | | | X | | | | X | | | | X | X |
| UD | | | X | | | | X | | | | X | |
| Brain, Cervical, and Thoracic MRI ±Gd | | | X | | | | X | | | | X | X |
| Twelve Item MS Walking Scale | | | X | | | | X | | | | X | X |
| Infectious disease test | X | | | | | | | | | | | |
| Pregnancy test (females) | X | | | | | | | | | | | |
| Drug & Nicotine Urine Testing | X ⁵ | | | | | | | | | | | |
| Urinalysis & Culture | | | X | | | | X | | | | X | |
| Bladder Survey | | | X | | | | X | | | | X | |
| Infectious Disease Questionnaire | X | | | | | | | | | | | |

¹Screening Blood Draw will include CBC with differential, ESR, Comprehensive Metabolic Panel, PT/PTT, and Thyroid Function Tests

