9.1 Study endpoints

9.1.1 Primary endpoint(s)

Primary efficacy outcome will be a composite score based on EDSS (our EDSS assessments will be based only on pyramidal and brainstem FSS, and performed by a blinded examiner), T25FW, and 9HPT (EDSS-Plus) [6]. Improvement will be defined by at least one of the following three measures: ≥ 0.5 improvement in EDSS (if EDSS at entry is ≥ 6.0) or ≥ 1.0 improvement in EDSS (if EDSS at entry is ≤ 5.5), $\geq 20\%$ improvement in T25FW, or $\geq 20\%$ improvement in 9HPT in either dominant or non-dominant upper limb. Scores will be compared within patients between the baseline and various post-treatment visits. Scores will also be compared between different treatment groups at various post-treatment visits. Assessments will be made at Baseline (within 4 months of first treatment/placebo), Month 6 (just prior to 4th

treatment/placebo), Month 13 (3 months post 6th treatment/placebo), Month 20 (just prior to 10th treatment/placebo), and Month 27 (3 months post 12th treatment/placebo). Long-term follow-up assessment will be conducted at Month 36. The primary outcome will be the comparison of the composite scores at Month 13 (3 months after the 6th treatment/placebo) compared to baseline.

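### The EDSS baseline for the primary endpoint is a screening score up to 4 months old, while T25FW and 9HPT are measured within 1 month of first treatment

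*Protocol*

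**What the plan says.** Protocol section 6.1 sets screening "within 4 months prior to first treatment" and introduces its examinations with "Subjects will then undergo the following examinations to confirm eligibility for study participation". A complete neurological examination and the EDSS are on that list without condition.

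Section 6.2 places the baseline visit "within one month prior to first treatment" and says: "The purpose of the baseline visit is to establish baseline values of outcome assessments prior to treatment". The EDSS entry at that visit nevertheless reads "EDSS-Only if not performed at screening", and the neurological exam carries the same condition. A footnote to the section 6.4 table repeats the exemption. The MSFC is unconditional at the baseline visit. Its table row, "MSFC (T25FW, 9HPT, PASAT", shows that it supplies T25FW and 9HPT, and it has no entry under screening.

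Protocol section 9.1.1 and SAP section 1.3.1 use one window for all three components: "Assessments will be made at Baseline (within 4 months of first treatment/placebo". A subject responds by improving on any one of them. The EDSS step required is 0.5 for entry scores of 6.0 or more and 1.0 for entry scores of 5.5 or less. On eligibility, Protocol section 4 states: "Disease stability will be determined by less than a 1.0-point change in EDSS in the last 12 months".

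**The concern.** The condition on the Month -1 EDSS is never met in a subject who followed section 6.1. The visit meant to set outcome baselines therefore sets none for the EDSS. That component falls back on the score used to admit the subject. One composite endpoint then has two baseline dates.

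This matters most at EDSS 6.0 and 6.5, where a single 0.5 step is a response. The stability rule treats a change of that size as stable. A step down between screening and the first procedure can appear at Month 13 as a response that treatment did not cause. A step up can conceal a real one. The plan also judges Month 13 against the baseline visit, which for most subjects will hold no EDSS value. For year 2 the plan does take a fresh EDSS, at Month 13, one month before the Month 14 procedure.

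**Working it through.** **Age of each baseline**
- EDSS: up to 4 months at first treatment (6.1). T25FW and 9HPT: up to 1 month (6.2). The gap is up to 4 - 1 = 3 months.
- Interval to Month 13: up to 13 + 4 = 17 months for the EDSS and up to 13 + 1 = 14 months for the timed tests.
- An age near 4 months is the planned case. Enrollment means consent (section 4), which is given at screening (6.1). The marrow visit follows about 1 month later and about 3 months before treatment (6.2), and 1 + 3 = 4. Section 6.2 also allows previously harvested marrow, and those subjects may have a shorter gap.

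**Subjects for whom 0.5 is a response**

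From the stratification table in Protocol section 3: (10 + 2) at EDSS 6.0 plus (10 + 2) at 6.5 = 24 of 50, or 48%.

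**The plan's own power figure**

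Inputs from Protocol section 9.2: 20 per group, 40% against 5% responders, two-sided pooled Z-test, alpha 0.05. Exact binomial enumeration of that test gives 82.0%, which agrees with the stated figure of more than 80%. The normal approximation gives 77.7%. Either way there is little margin.

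**Illustration**

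The share q is assumed; the documents give no figure. Let a share q of the subjects at 6.0 or 6.5 shift by 0.5 between screening and first procedure and hold the shift to Month 13, with the same q in both arms. A downward shift turns a non-responder into a responder, and an upward shift cancels a response. Let s = 0.48q.
- All improve: placebo = 0.05 + 0.95s; treated = 0.40 + 0.60s.
- Split equally: placebo = 0.05 + (s/2)(0.95 - 0.05); treated = 0.40 + (s/2)(0.60 - 0.40).
- All worsen: placebo = 0.05(1 - s); treated = 0.40(1 - s).

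In all three cases the true difference is 0.35(1 - s): 34.2, 33.3 and 31.6 percentage points for q = 5%, 10% and 20%. Power differs because the underlying rates differ.

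| q | All improve: placebo / treated, power | Split equally: placebo / treated, power | All worsen: placebo / treated, power |
|---|---|---|---|
| 0 | 5.0% / 40.0%, 82% | 5.0% / 40.0%, 82% | 5.0% / 40.0%, 82% |
| 5% | 7.3% / 41.4%, 76% | 6.1% / 40.2%, 78% | 4.9% / 39.0%, 81% |
| 10% | 9.6% / 42.9%, 71% | 7.2% / 40.5%, 75% | 4.8% / 38.1%, 79% |
| 20% | 14.1% / 45.8%, 62% | 9.3% / 41.0%, 67% | 4.5% / 36.2%, 77% |

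These are total effects of change before the first procedure. A Month -1 rating would recover only the part that arises before Month -1.

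**The case against.** The strongest reply is that the 4-month window is declared. Protocol 9.1.1 and SAP 1.3.1 agree on it, and it matches the screening window, so an analyst would not be misled. That stands as far as it goes: this is a disclosed choice, not a hidden error. It does not remove the mismatch between components or the conflict with the purpose given for the baseline visit.

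Three stronger readings are tempting, and the documents do not support them.
- *The stale baseline biases the comparison of arms.* Allocation is equal and stratified, the examiners are blinded, and one rule applies to both arms. The harm is dilution and noise.
- *Regression to the mean in an eligibility score must push the placebo rate above 5%.* Entry is bounded at both 3.0 and 6.5, and strata are filled to fixed numbers. The upper bound tends to admit subjects who were scored too low, and these would regress towards worsening. The disease is progressive, which also points towards hidden responses. Entry further requires disability that was not recently acquired, so it does not rest on one isolated score. The net direction is unknown.
- *Power drops to 62%.* That needs q = 20%, with every shift an improvement that is held to Month 13. The planned 5% may also already include such fluctuation, in which case adding q counts it twice.

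The reply is also right that a new rating does not remove rater noise or change in the last month before treatment.

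**Conclusion.** The point holds as a design weakness that should be corrected. In a compliant subject the EDSS component of the primary endpoint rests on an eligibility score up to 4 months old, and usually close to that, against at most 1 month for T25FW and 9HPT. In 48% of planned subjects one pre-treatment step of 0.5 can create or hide a response.

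The consequence is added noise and some loss of power and interpretability in both arms. Its size and net direction cannot be derived from the documents. Under the assumed q of 5% to 20%, power lies between 81% and 62%, depending on q and on the direction of the shifts. The year 2 baseline shows that the plan already accepts a one-month standard. It does not bear on the Month 13 comparison itself.

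**What to change.** - **Protocol 6.2 and the 6.4 table:** remove the condition, and perform the EDSS and its neurological exam at Month -1 in every subject.
- **Protocol 9.1.1 and SAP 1.3.1:** define the baseline EDSS for the change score as that value, taken within one month of first treatment or placebo. Say whether the screening or the Month -1 value sets the entry score that fixes the 0.5 or 1.0 threshold.
- **Unchanged:** the screening EDSS stays for eligibility and stratification, so randomization is not affected.
- **Subjects already past Month -1:** use the screening EDSS and report its age at first treatment. The SAP revision history anticipated initial analysis in December 2021, so this may apply to many subjects.

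The cost is one more rating per subject, at an existing visit already conducted by the examining neurologist, plus wording changes in both documents. Some subjects may have a baseline that differs from their stratum. A Month -1 score could also fall outside the entry range. Protocol sections 4, 8.4 and 13.1 all bear on a subject who meets an exclusion criterion during the study, and 8.4 and 13.1 disagree on whether such a subject is replaced. The sponsor must reconcile those sections and state how a Month -1 score of this kind is handled.

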- Details regarding treatment/placebo procedures detailed in section 5.2.2 above
- Treatment visits will be conducted by the treating neurologist, [name]
- Duration of treatment visits will last approximately 5 hours
- Study subjects will be instructed to stay in bed and limit any physical activity for the 24 hours following each procedure.
- CSF for biomarker analysis discussed in 5.2.2
- Blood draw for serum and plasma biomarker analysis
- Vital Signs
- EDSS and MSFC (Month 20 Only). Follow-up by phone will occur 48 hours, 1 week, and 1 month after each treatment visit. The purpose of the follow-up phone call is safety assessment and to document any adverse events. Calls will be made either by the clinical trial manager, the clinical research assistants, or the adverse event physician. Assessment will include the following:
- Headache pain scale

Outcome assessments II (Month 27):

- The purpose of outcome assessment II visit is to evaluate effects of the treatment group in year 2 compared to the baseline visit at the beginning of year 2. In addition, these assessments will be used to evaluate any sustained effects of the treatment in year 1.
- The following exams will be conducted 3 months following the 12th treatment visit (\pm 1 week) by the study subject's examining neurologist and study coordinator
- Vital signs
- Physical exam
- Neurological exam
- Headache pain scale
- EDSS
- MSFC
- 6 Minute Walk Test
- 12 Item MS Walking Scale
- Bladder Survey
- Urinalysis and Culture to screen for UTI
- Lumbar Puncture with CSF Aspiration for biomarker analysis
- Blood draw for serum and plasma biomarker analysis
- The following exams will be scheduled to occur 3 months following the 12th treatment visit (\pm 1 week)
- MRI (brain, C and T spine) \pm Gadolinium enhancement
- Urodynamic testing of bladder compliance (ability of bladder to fill without accompanying rise in bladder pressure)

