### 1.3 Primary and Secondary Outcomes

#### 1.3.1 Primary Outcome

Primary efficacy outcome will be a composite score based on EDSS (our EDSS assessments will be based only on pyramidal and brainstem FSS, and performed by a blinded examiner), T25FW, and 9HPT (EDSS-Plus). Improvement will be defined by at least one of the following three measures:  $\geq 0.5$  improvement in EDSS (if EDSS at entry is  $\geq 6.0$ ) or  $\geq 1.0$  improvement in EDSS (if EDSS at entry is  $\leq 5.5$ ),  $\geq 20\%$  improvement in T25FW, or  $\geq 20\%$  improvement in 9HPT in either dominant or non-dominant upper limb. Assessments will be made at Baseline (within 4 months of first treatment/placebo), Month 6 (just prior to 4th treatment/placebo), Month 13 (3 months post 6th treatment/placebo), Month 20 (just prior to 10th treatment/placebo), and Month 27 (3 months post 12th treatment/placebo). Long-term follow-up assessment will be conducted at Month 36. The primary outcome will be the comparison of the composite scores at Month 13 (3 months after the 6th treatment/placebo).

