### **4 STATISTICAL ANALYSIS OF THE PRIMARY AND SECONDARY STUDY OBJECTIVES**

#### **4.1 Analysis of the Primary Study Objective**

##### Primary Outcome:

The primary analysis will include all subjects meeting inclusion and exclusion criteria and who have completed a year of treatment/placebo and the 3 month post-treatment assessment. EDSS Plus composite score from 3 month post-treatment assessment will be compared to baseline.

Descriptive statistics will be calculated for patients at baseline for the entire cohort as well as by treatment status. Treatment and placebo group patients will be compared on continuous and discrete baseline characteristics to assess randomization.

The EDSS-Plus scale will be used as our primary endpoint with improvement on one or more of the 3 components (EDSS, T25FW and 9HPT). Improvement is defined as  $\geq 1$  point decrease from baseline EDSS if EDSS at entry is  $\leq 5.5$ , and a  $\geq 0.5$  point decrease from baseline EDSS if EDSS at entry is  $\geq 6.0$ ,  $\geq 20\%$  positive change in T25FW, and/or  $\geq 20\%$  positive change in 9HPT confirmed. The primary endpoint of improvement on one or more of the 3 EDSS-Plus categories between treatment and placebo groups will be assessed bi-varately using the chi-square or Fisher's exact test, as appropriate, at year 1, 2, and 3 of the study. Adjusted odds ratio (95%CI) between treatment and placebo groups at each time point will be estimated through mixed effect logistic regression with fixed effect of time, treatment, relevant covariates, and random effect of patients. The three components of the EDSS-Plus composite score will also be assessed individually at all time points. A longitudinal linear mixed-effect model will be used to assess longitudinal change (percentage change in mean time) from baseline to 3 years for T25FW and 9HPT, with random intercepts for patients and taking into account treatment status (treatment vs placebo), disease subtype (SPMS vs PPMS) and time-progression status interaction.

**Study Name:** Autologous, Bone Marrow-Derived Mesenchymal Stem Cell-Derived Neural Progenitor Cells, Expanded Ex Vivo; Administered Intrathecally (Phase II Trial)

**Principal Investigator:** [name]

Under parallel design, we will compare the outcomes of interest between the two study treatments, with outcomes at 1 year as the primary time point, secondary analyses will evaluate outcomes at years 2 and 3.

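### Protocol 6.2 makes Month 13 the reference for year-2 treatment, but neither protocol section 9 nor the SAP plans an analysis that uses it, so one of the two Month 27 questions goes unanswered.

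*Protocol*

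**What the plan says.** Protocol 6.2 gives Month 13 two roles. It closes year 1, and it is there "as well as to serve as a baseline visit for the crossover treatment phase". Month 27 also has two purposes. The first is to "evaluate effects of the treatment group in year 2 compared to the baseline visit at the beginning of year 2". The second is that "these assessments will be used to evaluate any sustained effects of the treatment in year 1".

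The analysis text has a single reference point. SAP 1.3.1 states: "Assessments will be made at Baseline (within 4 months of first treatment/placebo"; it names no other baseline. SAP 4.1 defines EDSS response as a "point decrease from baseline EDSS if EDSS at entry is" at or below 5.5 (1 point) or at or above 6.0 (0.5 point), with 20% changes in the timed tests. It says that "EDSS Plus composite score from 3 month post-treatment assessment will be compared to baseline". The resulting endpoint "will be assessed bi-varately using the chi-square or Fisher's exact test, as appropriate, at year 1, 2, and 3 of the study". On status, the SAP compares the two treatments "with outcomes at 1 year as the primary time point, secondary analyses will evaluate outcomes at years 2 and 3".

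Protocol 9.1.1 and 9.3 carry the same baseline and the same entry-based threshold. The mismatch therefore lies inside the protocol, between section 6.2 and section 9, as well as between protocol 6.2 and the SAP.

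**The concern.** By Month 27 both arms have had the cell course: one in year 1, the other in year 2. A response scored from study entry mixes what happened in the two years, and this can mislead in both sequences.

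- A placebo-first subject who worsens in year 1 and recovers on cells in year 2 can be scored a non-responder.
- A treatment-first subject who gained in year 1 and merely holds the gain is scored as improved while receiving year-2 placebo.

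Both errors pull the year-2 comparison towards no difference. The more durable the treatment, the less of a year-2 effect the entry-based score can show. The adjusted odds ratios in SAP 4.1 use the same outcome, so they inherit the problem at the later time points. If the reference visit stays open until year-2 data are seen, the choice between two rules that can disagree becomes post hoc.

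**Working it through.** **Single-subject checks under the plan's rules** (entry, Month 13, Month 27)

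- T25FW 10.0, 12.5, 10.0 s. From Month 13: (12.5 − 10.0)/12.5 = 20%, a response. From entry: (10.0 − 10.0)/10.0 = 0%, no response.
- EDSS 6.0, 6.5, 6.0. From Month 13: a gain of 0.5, a response. From entry: 0, no response.
- EDSS 6.0, 5.5, 5.5. From entry: a gain of 0.5, a response. From Month 13: 0, no response.
- EDSS 5.5, 6.5, 6.0. The gain from Month 13 is 0.5. It is a response if the Month 13 value (6.5) sets the threshold, and not if the entry value (5.5) does. The threshold rule therefore needs stating along with the reference visit.

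**The plan's own figure.** Inputs from SAP 1.5 and protocol 9.2: 40% vs 5%, 20 per arm, two-sided pooled Z-test, alpha 0.05. Exact binomial enumeration gives 82.0%, which reproduces the stated figure of more than 80%. Fisher's exact test gives 71.6%. Fisher is the likelier choice under SAP 4.1, because the smallest expected count is 20 × (0.40 + 0.05)/2 = 4.5. The plan states this power for the Month 13 primary and gives none for year 2.

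**Month 27 scored from entry.** Assumptions: 40% respond in a cell period and 5% in a placebo period, whichever year it falls in; no year-1 worsening; a share *s* of year-1 responses still present at Month 27. The documents give no value for *s*, so the full range is shown. The same carry-over rule applies to both arms:

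- Placebo-first: 0.05*s* + (1 − 0.05*s*) × 0.40 = 0.40 + 0.03*s*
- Treatment-first: 0.40*s* + (1 − 0.40*s*) × 0.05 = 0.05 + 0.38*s*
- Difference: 0.35 × (1 − *s*)

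| *s* | Placebo-first | Treatment-first | Difference (points) | Exact power, pooled Z | Fisher |
|---|---|---|---|---|---|
| 0 | 40.0% | 5.0% | 35 | 82.0% | 71.6% |
| 0.25 | 40.75% | 14.5% | 26.25 | 47.8% | 35.1% |
| 0.50 | 41.5% | 24.0% | 17.5 | 22.5% | 14.3% |
| 0.75 | 42.25% | 33.5% | 8.75 | 8.7% | 4.8% |
| 1 | 43.0% | 43.0% | 0 | 4.6% | 2.2% |

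**Month 27 scored from Month 13, same assumptions.** 40% vs 5%: 35 points, power 82.0% (pooled Z) or 71.6% (Fisher).

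**Adding year-1 worsening (illustrative).** Suppose half of the placebo-first subjects who respond to cells still miss the entry-based threshold because they declined first. Replacing 0.40 by 0.20 in the placebo-first formula gives:

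- *s* = 0: 20% vs 5%, +15 points, power 29% (pooled Z)
- *s* = 0.5: 22% vs 24%, −2 points
- *s* = 1: 24% vs 43%, −19 points

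**The case against.** The strongest reply is that entry-based scoring at Month 27 is not an error. The second stated purpose of that visit is sustained year-1 benefit, which needs the entry reference. A treatment-first subject who holds a gain is what that purpose looks for. This stands, and it is why the entry-based analysis should be kept. It does not supply an analysis for the first purpose.

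The stakes are also limited. SAP 1.2 describes a parallel-group design with a compassionate crossover, year 1 is primary, and years 2 and 3 are secondary. This stands too.

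Four stronger readings are tempting, and the documents do not support them.

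- *The SAP says that Month 27 is compared with entry.* No sentence says so. It follows from the single defined baseline, the entry-based threshold and the reuse of one endpoint at three years.
- *The year-2 effect will be lost.* Only if year-1 responses persist or placebo subjects worsen. Protocol 1.2 reports that some Phase I gains faded after the third dose, and Month 27 is 17 months after the last year-1 procedure at Month 10. Eligibility requires a stable MRI and less than a 1-point EDSS change in the previous 12 months, so year-1 decline cannot be taken for granted. With neither, nothing is lost.
- *Persistence alone reverses the sign.* A reader who lets the treatment-first arm keep old responses and add new ones (43%), but holds placebo-first at 40%, gets −3 points. Applying the same rule to both arms gives 0. Reversal needs year-1 worsening as well.
- *A paired test in placebo-first subjects (year 1 on placebo, year 2 on cells) should become the year-2 efficacy analysis.* It is confounded with time, is exposed to regression to the mean, and applies unequal EDSS thresholds within one subject if the threshold is reset at Month 13. The 82% is not its power: exact McNemar power for 20 subjects at 5% vs 40% is about 64% if the two responses are independent.

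**Conclusion.** The concern holds as a gap between a stated visit purpose and the planned analyses. Protocol 6.2 asks for year-2 treatment effects against Month 13, and neither protocol section 9 nor the SAP uses Month 13 as a reference.

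If the endpoint is applied as written, power to see a year-2 difference ranges from 82% to about 5% (72% to 2% with Fisher's test) as persistence of year-1 response goes from none to complete. Year-1 worsening on placebo lowers it further and can reverse the sign. These figures rest on the plan's 40% and 5% holding in both years, 20 analysed per arm, and a persistence share that is assumed.

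The Month 13 primary comparison and its power are unaffected. The change should be made before year-2 data are analysed, but it does not bear on the trial's main conclusion.

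**What to change.** In SAP 4.1 and protocol 9.3:

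1. Add a supportive between-arm analysis of Months 20 and 27 with response defined as change from Month 13.
2. State which EDSS value, entry or Month 13, sets the 0.5 or 1.0 threshold in that analysis.
3. Label the year-2 groups by the treatment received in that period. The current text leaves open whether treatment versus placebo at year 2 means the assigned arm or the current treatment.
4. Keep the entry-based analysis at years 2 and 3, and name it as the assessment of sustained effect.
5. Leave the Month 13 primary comparison unchanged.
6. If placebo-first subjects are compared with themselves across the two years, report it descriptively and use the same EDSS threshold in both periods.

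The cost is wording only, since EDSS and MSFC are already scheduled at Months 13, 20 and 27. The downside is that Month 13 is a post-randomisation reference that year-1 treatment may itself have shifted. The arms may start year 2 from different levels, so the added analysis can only be supportive.
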